## 7 ENDPOINTS AND ASSESSMENTS

In the endpoint definitions below, rescue therapy for roxadustat treated subjects is defined as ESA rescue or RBC transfusion and rescue therapy for epoetin alfa-treated subjects is defined as RBC transfusion.

All endpoints related to Hb are based on central lab values

### 7.1 Primary Endpoint:

- **US (FDA) submission:** Mean Hb change from baseline to the average level during the Evaluation Period, defined as Week 28 until Week 52. This analysis will be based on the intent-to-treat (ITT) population. Hemoglobin values under the influence of rescue therapy will not be censored for the primary analysis.
- **Ex-US submission:** The proportion of subjects who achieve a Hb response at two consecutive visits during the first 24 weeks of treatment, without rescue therapy within 6 weeks prior to the Hb response. This analysis is based on the Per Protocol Set (PPS) population.

A Hb response is defined, using central laboratory values, as

- Hb  $\geq 11.0$  g/dL and a Hb increase from baseline by  $\geq 1.0$  g/dL in subjects whose baseline Hb  $> 8.0$  g/dL, or
- Increase in Hb  $\geq 2.0$  g/dL in subjects whose baseline Hb  $\leq 8.0$  g/dL

### 7.2 Secondary Endpoints

- **US (FDA) submission:** The proportion of subjects who achieve a Hb response at two consecutive visits during the first 24 weeks of treatment, without rescue therapy within 6 weeks prior to the Hb response.

A Hb response is defined, using central laboratory values, as

- Hb  $\geq 11.0$  g/dL and a Hb increase from baseline by  $\geq 1.0$  g/dL in subjects whose baseline Hb  $> 8.0$  g/dL, or
- Increase in Hb  $\geq 2.0$  g/dL in subjects whose baseline Hb  $\leq 8.0$  g/dL

- **Ex-US submission:** Mean Hb change from baseline to the average level during the Evaluation Period, defined as Week 28 until Week 36 without rescue therapy within 6 weeks prior to and during the evaluation period. This analysis will be based on the PPS population.

Both, US and ex-US Submissions:

- Average monthly IV iron use per subject during the Treatment Period. Mean change in low-density lipoprotein (LDL) cholesterol averaged over Weeks 12 to 24.

- Blood pressure effects:
  - Proportion of subjects with exacerbation of hypertension, meeting at least one of the following criteria:
    - Increase in BP: An increase from baseline of  $\geq 20$  mm Hg systolic BP and sBP  $>170$  mmHg, or an increase from baseline of  $\geq 15$  mm Hg diastolic BP and dBP $>100$  mmHg. Increases from baseline in blood pressure must be confirmed by repeat measurement.
  - Time to an increase in BP as defined above.
  - Mean change in mean arterial pressure (MAP) averaged over Weeks 8 to 12.
- Time to achieve first Hb response as defined by the primary endpoint (ex-US) (which is the secondary endpoint for the US [FDA]).

### 7.3 Additional Evaluation of Efficacy

- **Hemoglobin Correction and Maintenance:**
  - Hemoglobin maintenance: Mean change in Hb averaged over 8 weeks of treatment at Weeks 28 to 52, without rescue therapy within 6 weeks prior to and during this 8-week evaluation period.
  - Hemoglobin long-term Maintenance: Mean change in Hb averaged over 8 weeks of treatment at Weeks 44 to 52 without rescue therapy within 6 weeks prior to and during this 8-week evaluation period
  - Mean change in Hb averaged over the 96 to 104 weeks of treatment, without rescue therapy within 6 weeks prior to and during this 8-week evaluation period
  - Change in Hb at each of the selected time points
  - Change in Hb averaged over 8 weeks of treatment at Weeks 28 to 36, without rescue therapy within 6 weeks prior to and during this 8-week evaluation period, in subjects who have reached a Hb  $\geq 11$  g/dL prior to Week 28
  - Proportion of subjects with Hb within 10 to 12 g/dL in United States and 10 to 13 g/dL in Ex-US averaged over Weeks 28 to 36, without rescue therapy within 6 weeks prior to and during this 8-week evaluation period
- **Hospitalizations:**
  - Occurrence (number) of hospitalization(s)
  - Proportion of subjects hospitalized
  - Number of days of hospitalizations per patient-exposure year (PEY)
- Missed dialysis sessions

- **Rescue Therapy Use:**
  - Proportion of subjects who receive RBC transfusions
  - Number of RBC packs per patient-month exposure to study medication
  - The proportion of subjects requiring ESA rescue therapy will be summarized
- **Changes in Cholesterol Levels:**
  - Change at each of the selected treatment time points in:
    - Total cholesterol
    - LOL/HDL ratio
    - Non-HDL cholesterol.
  - Proportion of subjects achieving LDL target of < 100 mg/dL averaged over Weeks 12 to 24 of treatment.

#### **Additional Blood Pressure Effects:**

- Proportion of subjects achieving blood pressure treatment goal in ESRD subjects (pre dialysis systolic BP < 140 mmHg systolic and diastolic BP < 90 mmHg) averaged over Weeks 12 to 28
- **HRQoL and EQ-5D-5L Benefits of Anemia Therapy:**

Mean change averaged over Weeks 12, 36 and 52 of treatment including those listed below.

  - *Vitality Subscale of SF-36:* In FAS subjects with baseline Vitality Subscore below 50
  - *Physical Component Scores of SF-36:*
    - In FAS subjects with baseline *physical component scores* below 40
    - In all FAS subjects
  - *Anemia Subscale (“Additional Concerns”) of Functional Assessment of Cancer Therapy-Anemia (FACT-An) Scores:*
    - In FAS subjects with baseline subscale scores below 55 (generally associated with fatigue)
      - In all FAS subjects
  - *Total FACT-An Scores:*
    - In FAS subjects with baseline FACT-An scores below 135
    - In all FAS subjects
  - *EQ-5D-5L Scores:* In all FAS subjects

- **Hepcidin, Iron, and HbA1c:**

- Change in serum hepcidin at each of the selected time points
- Change in serum ferritin at each of the selected time points, total and sub-grouped by baseline values of < 100 ng/mL, 100 to 400 ng/mL, and >400 ng/mL
- Change in TSAT at each of the selected time points, total and sub-grouped by baseline values of < 20%, 20% to 40%, and >40%
- Change in HbA1c level at each of the selected time points in all subjects, in subjects with history of diabetes

## 7.4 Safety Assessments and Endpoints

Study-specific safety will be assessed by evaluating the following:

- TEAEs, TESAEs, and clinically significant laboratory values from baseline
- Vital signs, ECG findings and clinical laboratory values

Safety interpretation will also be made based on analyses of composite endpoints derived from adjudicated events pooled across multiple studies in the roxadustat Phase 3 program. The members of an independent adjudication committee blinded to treatment assignment will adjudicate the following events in multiple phase 3 studies:

- Death from any cause, MI, stroke, congestive heart failure requiring hospitalization, unstable angina requiring hospitalization, hypertensive emergency, deep venous thrombosis, pulmonary embolism, and vascular access thrombosis.
- Various region-specific pooled analyses of composites of these adjudicated events, pooled across multiple studies will be conducted. The analyses of the adjudicated events will be detailed in the region-specific pooled SAPs.

**For US (FDA) Only:** The primary safety endpoint in this study is the Major Adverse Cardiac Event (MACE) composite endpoint, defined as time to first occurrence of death from all causes, MI, or stroke, for the purpose of being pooled across multiple similar studies in the Phase 3 program. None of the individual studies are powered to meet the MACE primary safety endpoint individually. The pooled MACE analysis is only for purposes of supporting a US FDA regulatory filing of roxadustat.

The above adjudicated safety events may also be used to support the pooled analyses of additional composite safety endpoints across multiple studies in the Phase 3 program, such as MACE+ (death, MI, stroke, congestive heart failure requiring hospitalization, and unstable angina requiring hospitalization), or a composite which consists of all of the adjudicated events.

## 8 STATISTICAL CONSIDERATIONS

### 8.1 Sample Size Determination

The sample size calculation is based on the primary endpoint for both the US (FDA) submission and Ex-US submission.

At least 600 subjects will be enrolled in this study. During the course of this study, which is being conducted in parallel with other Phase 3 studies, up to 1200 subjects may be enrolled for safety evaluation of roxadustat in comparison to epoetin alfa including adjudicated and prespecified safety events of interest (ie, all-cause death, MI, stroke, congestive heart failure requiring hospitalization, unstable angina requiring hospitalization, DVT, pulmonary embolism, vascular access thrombosis, and hypertensive emergency). The final number of patients to be enrolled will be based on the enrollment rate of other studies within the same indication, in order to optimize stopping these studies at a comparable time frame.

With at least 600 subjects, the study will provide at least 99% power to demonstrate statistical noninferiority of roxadustat versus ESA in the primary endpoint for US (FDA) submission (ie, specifically, Hb change from baseline to the average level during the evaluation period defined as Week 28 until Week 52). This assumes a difference (roxadustat minus ESA) of 0.30 g/dL, a noninferiority margin for this difference of 0.75 g/dL and a standard deviation of 1.25 g/dL. This endpoint will be analyzed using the ITT population for the US (FDA) submission.

The study will provide at least 99% power to demonstrate statistical noninferiority of roxadustat versus ESA in the primary endpoint outside of the United States (ie, the proportion of subjects who achieve a Hb response at two consecutive visits during the first 24 weeks of treatment). This assumes a 80% responder rate for both roxadustat and epoetin alfa, in order to support the primary efficacy analysis (ie, a noninferiority comparison in responder rate between roxadustat and epoetin alfa) and assuming a noninferiority margin of -15% for this difference (roxadustat minus epoetin alfa). This endpoint will be analyzed using the PPS population for the European Medicines Agency (EMA) submission.

Randomization will be stratified by the following three factors:

1. Geographical region (US vs. Ex-US)
2. Screening Hb values ( $\leq 8$  g/dL vs.  $> 8$  g/dL)
3. Cardiovascular/cerebrovascular/thromboembolic medical history (yes vs. no).

### 8.2 Analysis Populations

The following analysis populations will be used for the statistical analysis:

- Safety Population: The Safety Population consists of all subjects who received at least one dose of study treatment. All safety data will be tabulated using descriptive statistics. If treatment received during the study differs from the randomized treatment, the actual treatment arm will be used for the analysis.

- Intent-to-Treat population: The ITT population consists of all randomized subjects. The primary efficacy endpoint for the US (FDA) submission will be analyzed using this population. In addition, the superiority comparison of this endpoint for the US (FDA) submission will be performed using this population as well.
- Full Analysis Set: The FAS consists of all subjects who receive at least one dose of study drug and have at least one postdose Hb assessment. If treatment received differs from the randomized treatment, the randomized treatment arm will be used. Efficacy analysis for superiority will be conducted on the FAS population for the EMA submission.
- Per Protocol Set: The PPS consists of all randomized subjects who received at least 4 weeks of study treatment, have at least one postdose Hb assessment and are without major protocol violations. Criteria for PPS exclusion will be defined in the Statistical Analysis Plan (SAP). Non-inferiority analyses for the EMA submission will be based on the PPS.

### 8.3 Interim Data Cut

There are currently no plans to conduct an interim data cut..

Safety data and dosing decisions will be monitored on an ongoing basis. Additional ongoing review of safety data will be conducted by an independent DSMB ([Section 3.8](#)).

### 8.4 Statistical Analysis

Safety and efficacy data will be summarized and presented by treatment group and time point in summary tables. Descriptive statistics including number of subjects (N), means, standard deviations, medians, and minimum and maximum values will be presented for continuous variables. Counts and percentages will be presented for categorical variables. For efficacy endpoints, the standard error and 95% CIs will be presented as part of the descriptive summaries.

#### 8.4.1 Subject Enrollment and Disposition

A table will provide the number of randomized subjects (ITT), treated subjects (Safety population), FAS and PPS subjects and subjects who terminated the Treatment Period/study early along with the reason for ET.

#### 8.4.2 Demographics and Baseline Characteristics

Demographics (age, race, sex), baseline characteristics including stratification factors, and subject disease characteristics will be summarized for the Safety, ITT, FAS and PPS populations.

Descriptive statistics will be calculated for continuous variables (eg, age, weight, baseline Hb, body mass index) and frequency counts and percentages will be tabulated for categorical variables (eg, sex, race, Hb category, region, iron status, and history of cardiovascular disease or cerebrovascular disease) by treatment group and overall.

#### 8.4.3 Efficacy Analyses

Efficacy analysis for superiority will be conducted on the ITT population for US (FDA) submission and on the FAS population for Ex-US submission.

Efficacy analysis for non-inferiority will be conducted on the ITT population for US (FDA) submission and on the PPS population for Ex-US submission.

Hemoglobin results obtained from the central laboratory will be used for all efficacy analyses. Baseline Hb is defined as the mean of at least three central laboratory Hb values: the last two screening Hb values prior to randomization plus the one predose Hb value on Day 1 of the Treatment Period.

#### 8.4.3.1 Primary Efficacy Analysis

**US (FDA) Submission:** The primary efficacy endpoint for US (FDA) submission is defined as the mean Hb change from baseline to the average level during the Evaluation Period, defined as Week 28 until Week 52. The analysis will be based on the ITT population. Hb values under the influence of rescue therapy will not be censored for the primary efficacy analysis.

The primary hypothesis to be tested for the primary efficacy analysis is:

$H_0: Hb \text{ mean change from baseline to the average level from Week 28 to Week 52 in the roxadustat arm} \leq Hb \text{ mean change from baseline in the epoetin alfa arm minus } 0.75 \text{ g/dL}$

*Versus:*

$H_1: Hb \text{ change from baseline to the average level of Week 28 to Week 52 in the roxadustat arm} > Hb \text{ mean change from baseline in the epoetin alfa arm minus } 0.75 \text{ g/dL}$

A Multiple Imputation Analysis of Covariance (MI ANCOVA) model will be used for the primary endpoint (change from baseline in Hb from Week 28 to Week 52).

The model will contain terms for treatment arm, baseline Hb measurement, and randomization stratification factors, except for Screening Hb values ( $\leq 8\text{g/dL}$  vs.  $> 8\text{g/dL}$ ). Detailed analysis of the primary [efficacy] endpoint will be outlined in the SAP. The primary efficacy analysis for US [FDA] and sensitivity analysis for the first secondary endpoint for ex-US submissions will be based on the estimated difference between the two treatment arms of the overall mean effects throughout the evaluation period based on the MI ANCOVA model.

In addition, as a sensitivity analysis, the primary efficacy endpoint for US [FDA] and primary analysis for the first secondary endpoint for ex-US submissions will be analyzed using the analysis of a model for repeat measures (MMRM). The MMRM model will contain terms for baseline Hb, as covariate, treatment arm, visit, visits by treatment arm, and randomization stratification factors (except for Screening Hb values ( $\leq 8\text{g/dL}$  vs  $> 8\text{g/dL}$ ) as fixed effects. Additional analysis using pattern mixture approaches would be detailed in the SAP.

Due to the large amount of visits to include in the model, the unstructured covariance pattern model will be tested against the less parameterized heterogeneous Toeplitz structure using the likelihood ratio test for nested models. If the algorithm for unstructured covariance pattern does not converge or the likelihood ratio test is not statistically significant then heterogeneous Toeplitz structure will be used. If this second model does not converge either, then the (homogeneous) Toeplitz structure will be tried and finally compound symmetry as a covariance structure to achieve convergence.

This null hypothesis will be rejected if the two-sided 95% CI for the difference (roxadustat minus epoetin alfa) of two least square means from the mixed model lies entirely above  $-0.75 \text{ g/dL}$ .

Hb values under the influence of a rescue therapy will not be censored in the primary analysis.

**Ex-US Submission:** The primary efficacy endpoint for Ex-US submission is defined as the proportion of subjects who achieve a Hb response at two consecutive visits during the first 24 weeks of treatment, without rescue therapy within 6 weeks prior to the Hb response.

- A Hb response is defined, using central laboratory values, as:  $Hb \geq 11.0 \text{ g/dL}$  and a Hb increase from baseline by  $\geq 1.0 \text{ g/dL}$  in subjects whose baseline  $Hb > 8.0 \text{ g/dL}$ , or
- Increase in  $Hb \geq 2.0 \text{ g/dL}$  in subjects whose baseline  $Hb \leq 8.0 \text{ g/dL}$

Rescue therapy for roxadustat treated subjects is defined as ESA rescue or RBC transfusion, and rescue therapy for epoetin alfa treated subjects is defined as RBC transfusion.

The hypothesis to be tested for the primary efficacy analysis is:

$H_0: Hb \text{ response rate for subjects in the roxadustat arm} - Hb \text{ response rate for subjects in the epoetin alfa arm} \leq -15\%$

*Versus*

$H_1: Hb \text{ response rate for subjects in the roxadustat arm} - Hb \text{ response rate for subjects in the epoetin alfa arm} > -15\%$

A two-sided 95% CI for the difference of 2 responder rates (roxadustat minus epoetin alfa) based on the Miettinen & Nurminen approach adjusting for treatment and other stratification factors will be calculated and this null hypothesis will be rejected if the lower bound of the 95% CI is greater than -15%.

The stratification factors to be used in efficacy analyses are:

1. Geographical region
2. Screening Hb values ( $\leq 8 \text{ g/dL}$  vs.  $> 8 \text{ g/dL}$ )
3. Cardiovascular/cerebrovascular/thromboembolic medical history (Yes vs. No)

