	
 
• Treatment Period: Treatment duration is variable for individual subjects. In order to complete the Treatment Period simultaneously for all study subjects, the minimum treatment duration may be less than 52 weeks with a maximum treatment duration of up to approximately 3 years after the last subject is randomized. Subjects will be informed at least 4 weeks prior to their treatment period end.
 
• Post-Treatment Follow-Up Period: 4 weeks
 
 
A total of up to approximately 1200 subjects will be randomized to receive either roxadustat or Active Control (epoetin alfa) in a 1:1 ratio (Appendix 1).
 
Randomization is stratified by geographical region, screening Hb values, and cardiovascular/cerebrovascular/thromboembolic medical history.
 
Scheduled Visits During Treatment
 
During the Treatment Period, subjects will attend weekly study visits from Weeks 0 to 4, followed by every other week study visits starting Week 6 until Week 24. Starting with Week 28, subjects will attend study visits every 4 weeks until the end of the Treatment Period.
 
After the Treatment Period, subjects will proceed to the 4-week Post-Treatment Follow-up Period.
 
Starting Dose of Study Drug
 
Roxadustat Arm
 
For subjects receiving roxadustat, the initial dose (per dose amount) is based on a tiered, weight-based dosing scheme (Table S1). Roxadustat will be dosed orally three times weekly (TIW) throughout the Treatment Period, except if a subject requires < 20 mg TIW (ie, < 60 mg per week) to maintain an Hb levels in the Maintenance Phase, the dosing frequency should be reduced in a step-wise fashion eg, TIW to BIW, BIW to QW, QW to Q-2 Week etc..
 
Epoetin Alfa Arm
 
 
• Subjects on hemodialysis (HD) receiving epoetin alfa will initiate IV epoetin alfa treatment according to the epoetin alfa US Package Insert (USPI) or Summary of Product Characteristics (SmPC).
 
• For subjects on home-hemodialysis (HHD) or peritoneal dialysis (PD), epoetin alfa will be administered according to the epoetin USPI or SmPC, or local standard-of-care.
 

--	---

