### 3.2 Randomization and Treatment Assignment

A total of up to approximately 1200 subjects will be randomized in a 1:1 ratio to receive either open-label roxadustat or epoetin alfa ([Appendix 1](#)).

Randomization is stratified by the following factors:

- Geographical region
- Screening Hb values ( $\leq 8$  g/dL vs.  $> 8$  g/dL)
- Cardiovascular/cerebrovascular/thromboembolic medical history (Yes vs. No)

Randomization schedules will be prospectively prepared. Automated randomization and treatment assignments will be provided by an Interactive Voice and Web Response System (IXRS).

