5 GENERAL STATISTICAL CONSIDERATIONS

5.1 SAMPLE SIZE DETERMINATION

The sample size calculation is based on the primary endpoints for the US (FDA) submission and Ex-US submission.

During the course of this study, which is being conducted in parallel with other Phase 3 studies, approximately 1000 subjects were to be enrolled to contribute to safety evaluation of roxadustat in comparison to epoetin alfa in CKD patients on dialysis less than 6 months. The final number of patients to be enrolled in this study will be based on the enrollment rate of other roxadustat phase 3 studies on dialysis patients, in order to optimize program timeline to generate sufficient adjudicated safety data across dialysis studies.

With at least 600 subjects, the study will provide at least 99% power to demonstrate statistical non-inferiority of roxadustat versus ESA in the primary endpoint for US (FDA) submission (i.e., specifically, Hb change from baseline to the average level during the evaluation period defined as Week 28 until Week 52). This assumes a difference (roxadustat minus ESA) of -0.30 g/dL, a non-inferiority margin for this difference of -0.75 g/dL (see Appendix 6 for the NI margin justification) and a standard deviation of 1.25 g/dL. This endpoint will be analyzed using the ITT population for the US (FDA) submission.

The study will provide at least 99% power to demonstrate statistical non-inferiority of roxadustat versus ESA in the primary endpoint outside of the United States (i.e., specifically, the proportion of subjects who achieve a Hb response at two consecutive visits during the first 24 weeks of treatment, without rescue therapy within 6 weeks prior to the Hb response). This assumes an 80% responder rate for both roxadustat and epoetin alfa, in order to support the primary efficacy analysis (i.e., a non-inferiority comparison in responder rate between roxadustat and epoetin alfa) and assuming a non-inferiority margin of -15% for this difference (roxadustat minus epoetin alfa).

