11.1.3.1 MMRM Model

A mixed model of repeated measures (MMRM) will be used as one sensitivity analysis for the primary endpoint for US Submission (change from baseline in Hb from Week 28 to Week 52).

The model will contain terms for treatment arm, baseline measurement, visit (up to Week 52), visit by treatment interaction, and stratification factors except Screening Hb values (≤ 8 g/dL vs. > 8 g/dL). The primary efficacy analysis (for US [FDA]) will be based on the estimated difference between the two treatments overall mean effects throughout the evaluation period based on the MMRM model. Hb values under the influence of a rescue therapy will not be censored in the primary analysis.

Due to the large amount of visits to include in the model, data up to Week 52, the unstructured covariance pattern model will be applied first. If the algorithm for unstructured covariance pattern does not converge or the likelihood ratio test is not statistically significant then heterogeneous Toeplitz structure will be used. If this second model does not converge either then the (homogeneous) Toeplitz structure will be tried and finally compound symmetry as a covariance structure to achieve convergence. If none of them converge, first order autoregressive (AR (1)) as a covariance structure will be used to achieve convergence.

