11.2.1.5 Mean change in mean arterial pressure (MAP) averaged over Weeks 8-12

Mean Arterial Pressure (MAP) will be calculated for each subject using the following formula: $MAP = (2/3) * DBP + (1/3) * SBP$.

Mean change from baseline in MAP will be analyzed and compared between the 2 treatment groups using an MMRM model with baseline MAP as a covariate, treatment group, visit, interaction of visit and treatment group, and above-mentioned stratification factors as fixed effects. The same strategy as that used in MMRM for Hb will be used to choose variance covariance structure. Data up to visit of Week 52 will be included in the model. The estimates for difference of MAP averaged over Weeks 8 to 12 between the two treatment groups will be generated from an estimate statement from Visit Week 8 to 12. Non-inferiority margin for the difference between groups is 1mmHg. Superiority will be declared if the upper bound of the 2-sided 95% confidence interval of the difference between roxadustat and ESA (roxadustat – ESA) is below 0.

11.2.1.6 Time to first exacerbation of hypertension over Week 28 to 52

Subject with exacerbation of hypertension is defined as meeting the following criterion:

Increase in blood pressure: An increase from baseline of ≥ 20 mm Hg systolic BP and sBP ≥ 170 mmHg or an increase from baseline of ≥ 15 mm Hg diastolic BP and dBP ≥ 100 mmHg. Increases from baseline in blood pressure are considered as confirmed by taking the mean of triplicates.

An exacerbation of hypertension is defined as an increase from baseline of ≥ 20 mm Hg systolic BP and sBP > 170 mmHg or an increase from baseline of ≥ 15 mm Hg diastolic BP and dBP > 100 mmHg).

Time to an exacerbation of hypertension in blood pressure will be analyzed and compared between the 2 treatment groups using the Cox Proportional Hazards model adjusting for baseline stratification factors. Both Non-inferiority and Superiority of roxadustat vs. ESA will be tested. The Non-inferiority margin for the difference between groups is 1.3 and the superiority margin for the difference between groups is 1. Subjects will be censored at the time of the last available blood pressure if an increase in blood pressure does not occur.

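### If the unstructured covariance fails for the 21-visit Hb mixed model, the fallback structures ignore the unequal visit spacing and no empirical standard error is planned, so the ex-US confidence interval depends on which structure converges

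*Protocol*

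**What the plan says.** **Visits.** According to the Protocol Synopsis, "subjects will attend weekly study visits from Weeks 0 to 4, followed by every other week study visits starting Week 6 until Week 24"; from Week 28 the visits are every 4 weeks. SAP 11.1.3.1 puts all data up to Week 52 into the Hb mixed model.

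**Covariance.** Protocol 8.4.3.1 tests unstructured against heterogeneous Toeplitz by likelihood ratio. It moves to heterogeneous Toeplitz if unstructured does not converge or if the test is not significant. After that: "If this second model does not converge either, then the (homogeneous) Toeplitz structure will be tried and finally compound symmetry as a covariance structure". SAP 11.1.3.1 keeps this order and adds a last step: "If none of them converge, first order autoregressive (AR (1)) as a covariance structure will be used to achieve convergence". Neither document mentions an empirical variance estimator or a structure based on elapsed time.

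**Role of the model.** Protocol 8.4.3.1 makes it a sensitivity analysis for the US primary endpoint and the primary analysis for the ex-US first secondary endpoint. The decision rule is on an interval: "This null hypothesis will be rejected if the two-sided 95% CI for the difference (roxadustat minus epoetin alfa) of two least square means" lies above -0.75 g/dL. SAP Table 5 places the ex-US test first in the fixed sequence. The covariance rule is reused, for example in SAP 11.2.1.5: "The same strategy as that used in MMRM for Hb will be used to choose variance covariance structure".

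**The concern.** With a Toeplitz structure, Weeks 1 and 2 must have the same correlation as Weeks 48 and 52, because both pairs are adjacent visits. AR(1) does the same with a single parameter. Compound symmetry gives every pair of visits the same correlation, whatever the distance. If Hb values a few weeks apart are more alike than values many weeks apart, none of these can fit, and a model-based standard error inherits the misfit.

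The ex-US first secondary test compares a confidence limit from this model with -0.75 g/dL. An interval that is too narrow raises the chance of a false non-inferiority claim. One that is too wide makes it harder to open the rest of the sequence. When unstructured does not converge, the likelihood-ratio check cannot be made, so nothing in the plan would reveal the misfit.

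**Working it through.** **1. The plan's own figure.** Protocol 8.1: "With at least 600 subjects, the study will provide at least 99% power to demonstrate statistical noninferiority of roxadustat versus ESA". The inputs are 1:1 allocation, so 300 per arm; SD 1.25 g/dL; margin -0.75 g/dL; and, from SAP 5.1, "This assumes a difference (roxadustat minus ESA) of -0.30 g/dL".
- SE = 1.25 x sqrt(2/300) = 0.102.
- Power = Phi((0.75 - 0.30)/0.102 - 1.96) = 99.3%. The stated figure is reproduced.

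**2. Size of the model.** Weeks 1-4 give 4 visits, Weeks 6-24 give 10 and Weeks 28-52 give 7: 21 in all.
- Unstructured: 21 x 22/2 = 231 parameters.
- Heterogeneous Toeplitz: 21 variances + 20 correlations = 41.
- Toeplitz: 21. Compound symmetry: 2.
- Actual time pooled under one Toeplitz lag: lag 1 covers 1, 2 and 4 weeks; lag 2 covers 2 to 8 weeks; lag 3 covers 3 to 12 weeks.

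**3. One worked case.** Assumed truth: SD 1.25 at every visit, correlation 0.2 + 0.8 x 0.6^(weeks/4), complete data. Each structure S is fitted to the true covariance V by minimising log|S| + tr(S^-1 V), the large-sample likelihood limit. The target is the average over Weeks 28, 32 and 36.
- True correlations: 0.68 at 4 weeks and 0.488 at 8 weeks. True SD of the average = 1.25 x sqrt[(3 + 2(0.68 + 0.68 + 0.488))/9] = 1.078.
- Compound symmetry: the fitted correlation is the mean over all visit pairs, 0.386. SD = 1.25 x sqrt[(1 + 2 x 0.386)/3] = 0.961. Ratio 0.961/1.078 = 0.89.
- Heterogeneous Toeplitz: the short early gaps push the lag-1 and lag-2 correlations up to 0.81 and 0.67, and the fitted SDs at these visits become 1.52-1.57. SD of the average 1.417. Ratio 1.31.
- Toeplitz 1.134/1.078 = 1.05. AR(1) 1.130/1.078 = 1.05.

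**4. Range over assumptions.** Calculations of this kind were repeated with faster and slower decay, with and without a persistent component and measurement noise, with SD flat, rising early or higher before Week 28, and with no dropout or 35% dropout unrelated to outcome. Weeks 28-36 and 28-52 were both covered, because SAP 4.3 names the first window for the ex-US endpoint and SAP Table 5 the second. One-sided error is P(Z > 1.96 x ratio).

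| Structure | Model SE / true SE | One-sided error (nominal 2.5%) |
|---|---|---|
| Heterogeneous Toeplitz | about 1.1-1.4 | 1.6% to 0.3% |
| Toeplitz, AR(1) | about 0.85-1.2 | 4.8% to 0.9% |
| Compound symmetry | mostly 0.7-0.95 | 8.5% to 3.1% |

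The lowest compound symmetry ratio actually obtained was 0.71, which gives 8.2%. In the one set of scenarios where SD was higher before Week 28, compound symmetry gave 0.98-1.06.

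**5. Simulation, 300 per arm, 35% dropout, compound symmetry (1000 replicates).** Coverage of the nominal 95% interval was 89.7% and 89.9% (Weeks 28-52 and 28-36) with flat SD, and 85.1% and 86.3% with SD rising early. With the sandwich standard error it was 94.5-95.2%. A 60-replicate run for heterogeneous Toeplitz at Weeks 28-52 gave model SE over empirical SD of 1.20 and sandwich SE over empirical SD of 0.96. That is too few replicates for a coverage statement.

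**The case against.** **The plan has a guard when unstructured converges.** This stands. In the step 3 case with 600 subjects, the likelihood-ratio statistic against heterogeneous Toeplitz has 231 - 41 = 190 degrees of freedom and noncentrality about 380. Its expected value of 570 compares with a 5% critical value of 223, so unstructured would be kept. The problem needs actual non-convergence, and the documents give no probability for that.

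**The structures do not carry equal risk.** This also stands. The first fallback was conservative in every scenario. Compound symmetry is reached only after unstructured, heterogeneous Toeplitz and Toeplitz have all failed, and AR(1) only after a fourth failure.

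**Power.** A reader might multiply the planning SE of 0.102 by 1.34 and infer that power falls to Phi(0.45/0.102 - 1.96 x 1.34) = 96.3%. The documents do not support this. They use 1.25 as the SD of the averaged change, whereas the inflation was derived with 1.25 at each single visit. In the step 3 case the matching SE is 1.078 x sqrt(2/300) = 0.088, and power is Phi(0.45/0.088 - 1.96 x 1.31) = 99.4%. Over five decay scenarios it is 98.9-99.8% for Weeks 28-36 and 99.7-100% for Weeks 28-52.

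**Reach.** A reader might infer from the mixed-model wording of the rejection rule in Protocol 8.4.3.1 that the US primary result is exposed. It is not: that section and SAP 11.1.2 both make MI ANCOVA the primary analysis. MI ANCOVA is also the prespecified sensitivity analysis for the ex-US endpoint. Among the other models that reuse the rule, lipids have 7 visits to Week 52 (28 parameters), iron indices 8 (36) and quality of life 3, so convergence failure is a realistic worry mainly for Hb and mean arterial pressure.

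**Conclusion.** The concern holds, within limits. If unstructured does not converge, the interval tested against -0.75 g/dL rests on a structure that ignores elapsed time, with no correction to its standard error. The error is about 10-40% too wide under heterogeneous Toeplitz, can go either way under Toeplitz and AR(1), and is mostly 5-30% too narrow under compound symmetry, where one-sided error can reach about 6-8%.

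These sizes rest on assumed correlations that decay with time. If correlation is constant over time, the error vanishes. The harm is to interval coverage and type I error in the ex-US first secondary test, to the US sensitivity analysis and possibly to mean arterial pressure. The plan's claim of at least 99% power is not materially affected. This is a cheap improvement to a contingency rule and does not threaten the main US result.

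**What to change.** In Protocol 8.4.3.1 and SAP 11.1.3.1, state that whenever a covariance structure other than unstructured is used, standard errors and confidence intervals come from the empirical (sandwich) estimator. The sections that reuse the rule then inherit it.

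The cost is one sentence in each document and one procedure option. Small-sample degrees-of-freedom corrections are lost, which is immaterial at about 300 per arm. The sandwich corrects the standard error only. If dropout depends on earlier Hb, a misfitting covariance can also bias the estimated difference.

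Optionally, add to the list a structure based on actual weeks with visit-specific variances; in the two scenarios checked, its ratio was 0.95-0.99. This takes more programming. The existing list should not simply be replaced by ordinary spatial power, which gave ratios of 0.86-1.00 in five scenarios and so tends to be anti-conservative where the present first fallback is conservative.
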